8.4 Efficacy analysis

8.4.1 The primary endpoints

The change value of HbA1c levels from baseline to 24 Weeks or before antidiabetic therapy initiation within 24 weeks will be analyzed using covariance(ANCOVA) model use the treatment group(XZK, atorvastatin) as the group and the baseline HbA1c as the covariate. The results will be presented as least squares means (lsmeans) with 95% confidence intervals and p-values. Model assumptions will be explored and, if necessary, appropriate transformations or non-parametric analysis techniques will be used. The primary analysis set for this analysis is the full analysis set (FAS).

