- (9) Other endocrine diseases that might influence the levels of lipid or lipoprotein, such as hypothyroidism.
- (10) Patient has participated in clinical trials of other drugs in the past three months.
- (11) Previous statin treatment causes creatine kinase (CK) increased 10 times, or myalgia myopathy (muscle pain or muscle weakness, accompanied by

	
Creatine phosphokinase (CK) exceeds 10 times the ULN)
 
(12)Estimated life expectancy < 6 months at the time of enrollment
 
(13)Abuse of alcohol, or history of alcohol abuse.
 
(14)Close affiliation with the investigators, e.g., a close relative for the investigator, dependent person (e.g., employee or student of the investigators)

Visit plan	5 visits: including enrollment period, baseline period, 4 weeks, 12 weeks and 24 weeks after randomization
Statistical Analyses	
Analyses will be performed by SAS 9.4 statistical software.
 
Descriptive statistics will be calculated, including n, means, standard deviations, medians, and interquartile ranges for continuous variables and frequency counts and percentages for categorical variables.
 
Percentage will be calculated based on non-missing data unless otherwise specified. Data will be examined for skewness, outliers.
 
Transformations will be undertaken as needed.
 
Missing data will be assumed missing completely at random. In general, no imputation will be applied unless otherwise specified. The primary and secondary endpoint will be analyzed using covariance(ANCOVA) model with treatment (XZK, atorvastatin) use the baseline HbA1c as the covariate.

Data collection	Case report form (CRF)

TABLE OF CONTENTS

STUDY PROTOCOL SUMMARY..... 2

TABLE OF CONTENTS 6

LIST OF ABBREVIATIONS AND DEFINITION OF TERMS..... 11

1 INTRODUCTION..... 13

1.1 Background 13

1.2 Rationale for study design 13

1.3 Benefit/risk and ethical assessment 15

1.4 Study Design 17

 1.4.1 Overall design 17

 1.4.2. Randomization 17

 1.4.3. Minimizing Sources of Bias 17

 1.4.4 Number of Centers 17

 1.4.5 Number of Participants..... 17

 1.4.6 Estimated Study Duration 17

 1.4.7 Study Duration for Participants..... 18

 1.4.8 End of Study..... 18

2 STUDY OBJECTIVES 18

2.1 Primary Objective 18

2.2 Secondary Objective 18

2.3 Safety 19

3 STUDY POPULATION 19

3.1 Inclusion Criteria..... 19

3.2 Exclusion Criteria..... 20

3.3 Subject enrolment and randomization 21

3.3.1 Number of Centers	21
3.3.2 Number of Participants.....	21

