1.2 Rationale for study design

Up to now, there is no published RCTs to compare the impact of XZK and statins on glucose metabolism in Prediabetes with dyslipidemia. However, systematic reviews of several large observational studies have recently

found statin treatment is associated with a modest increase in HbA1c in patients with T2DM. In these patients, the mean difference of HbA1c increased by 0.17% (95% CI 0.07, 0.27) compared with the blanking control group[7]. For instance, Atorvastatin 20mg is widely used medium intensity statin in clinical practice, but a cohort study based on a database of Korea populations reported that the use of low dose Atorvastatin 10-20mg tended to be a risk factor for onset diabetes (NODM) in Asians[8]. Meanwhile, a small RCT reported that HbA1c level was increased from 6.1% to 6.5% after Atorvastatin 20mg/d treatment for 2 months[9]. The long-term administration of statins might increase the risk of NODM approximately 10%-12%[10]. In short, a diabetogenic role of statins has been demonstrated both from randomized trials and meta-analyses, and risk factors include high dose, prolonged exposure, old age, prediabetic state and metabolic syndrome[11, 12]. In consideration of prediabetes, including IFG, IGT, or A1C 5.7–6.4%, will be further increased the risk of development diabetes mellitus, and the prevalence was 35.7% in China, we choose the patients in Prediabetes with dyslipidemia in our study[4].

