1.4.2. Randomization

Randomization of participants that meet all inclusion criteria and do not have any exclusion criteria will be randomly allocated in a 1:1 ratio to XZK group (xuezhikang [1200mg/d]) or ATV group (atorvastatin [20mg/d]) stratified by center and age(≥ 60 years old, < 60 years old) Randomization will be done using a central, automated, web-based electronic randomization software. Randomization will occur within 3 days after the Laboratory result of randomization visit reported .

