8 STATISTICAL ANALYSES

8.1 Sample size estimate

The primary endpoint of the study is the change value of HbA1c levels from baseline to 24 Weeks or before antidiabetic therapy initiation within 24 weeks.

We assume that the HbA1c level doesn't change in XZK group, and an increase of HbA1c level by 0.3% in atorvastatin 20mg group based on findings from Koh K et al. The SD of change of HbA1c level is 1.0% for both treatment.

The sample size of each group of 176 will provide 80% power at a 5% significance level. Considering 10% drop out rate, the total sample size is 392.

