8.3 Definitions of analysis sets

The full analysis set (FAS) includes all randomized subjects who received at least 1 dose of IP (investigational product) and have a non-missing HbA1c value at week 24. This analysis set will be used in both efficacy and safety analyses.

The Completer Analysis Set (CAS) includes subjects in FAS who completed IP and have a non-missing HbA1c value at week 24.

In all analysis sets, unless specified otherwise, subjects will be analyzed according to the ITT principle.

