8.4.2 Secondary endpoints

For each secondary endpoint, an ANCOVA model will be used that is similar to the one described for the primary analysis above.

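### Randomisation is stratified by centre and age, but the primary ANCOVA includes neither, so the test is conservative to the extent that they predict HbA1c change

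*Protocol*

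**What the plan says.** Section 1.4.2 says that patients are "randomly allocated in a 1:1 ratio to XZK group" or the atorvastatin group, "stratified by center and age", with age split at 60 years. Sections 1.4.4 and 3.3.1 expect about 20 sites. That makes about 40 centre-by-age cells, or roughly 10 patients per cell (392/40 = 9.8).

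Section 8.4.1 sets the primary ANCOVA to "use the treatment group(XZK, atorvastatin) as the group and the baseline HbA1c as the covariate". The synopsis agrees: "The primary and secondary endpoint will be analyzed using covariance(ANCOVA) model with treatment (XZK, atorvastatin) use the baseline HbA1c as the covariate". Section 8.4.2 extends the approach to each secondary endpoint: "an ANCOVA model will be used that is similar to the one described for the primary analysis above".

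The strata appear in the analysis only twice. Section 8.5 fits the same age split with a treatment interaction as a subgroup analysis, and section 8.4.3 tabulates adverse events by stratification factor. The protocol does not explain why they are absent from the primary model.

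**The concern.** Stratified allocation balances the strata between the arms. Whatever outcome variance the strata carry is then largely removed from the true sampling variance of the treatment difference. A model without those terms keeps this variance in its residual. The reported standard error then describes a less precise experiment than the one that was run.

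The possible loss is precision: a confidence interval that is wider than it need be, and a test that uses less than its 5%. The sponsor judged centre and age important enough to stratify on, and the stated primary model then ignores them.

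This is more than detail left to a statistical analysis plan, because the protocol names the covariate in two places. A plan that followed the wording would omit the strata, and a plan that added them would depart from the protocol's primary model.

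**Working it through.** **Inputs.** From section 8.1: difference 0.3 HbA1c points, SD of change 1.0, 5% significance, 80% power, 176 per group, 10% dropout. Sidedness is not stated, but two-sided reproduces the sample size. Assumed, because the protocol does not give it: R², the share of residual variance (after baseline HbA1c) due to centre and age, taken as 0, 5% and 10%. The residual SD is held at 1.0.

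**The plan's own figure.** Section 8.1 says "The sample size of each group of 176 will provide 80% power at a 5% significance level".
- Normal formula: n = 2(1.960 + 0.842)² × 1.0²/0.3² = 174.4, so 175 per group.
- With the t distribution, power is 0.799 at 175 and 0.801 at 176, which gives 176.
- Dropout: 176/0.9 = 195.6, so 196 per group and 392 in total. Both stated figures reproduce.

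**Formulas, strata perfectly balanced (upper end of the effect).** Let c = √(1 − R²) and s = √(2/176) = 0.1066. The unadjusted model reports s, while the true standard error is c·s.
- SE overstatement: 1/c − 1
- Type I error, unadjusted: 2[1 − Φ(1.96/c)]
- 95% CI half-width: 1.96s unadjusted, 1.96cs adjusted
- Power, unadjusted: Φ[(0.3 − 1.96s)/(cs)]
- Power, adjusted: Φ[0.3/(cs) − 1.96]
- n per arm for 80% power: 2(1.96 + 0.842c)²/0.09 unadjusted, 174.4c² adjusted

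| R² | SE overstated | Type I error, unadjusted | Half-width, unadj. vs adj. | Power, unadj. vs adj. | n per arm, unadj. vs adj. |
|---|---|---|---|---|---|
| 0 | 0 | 5.0% | 0.209 vs 0.209 | 80.4% vs 80.4% | 174.4 vs 174.4 |
| 5% | 2.6% | 4.4% | 0.209 vs 0.204 | 81.0% vs 82.3% | 171.8 vs 165.7 |
| 10% | 5.4% | 3.9% | 0.209 vs 0.198 | 81.6% vs 84.3% | 169.1 vs 157.0 |

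The last column corresponds to 2 × 6.1 ≈ 12 patients in total at R² = 5% and 2 × 12.1 ≈ 24 at R² = 10%. With fixed centre effects and 352 − 23 = 329 residual degrees of freedom, adjusted power by non-central t is 80.1%, 82.1% and 84.1%. Unadjusted power rises above 80% only because total SD is held at 1.0 while R² grows.

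**Simulation.** Small cells, incomplete blocks and dropout weaken the balance that the formulas assume. Settings: 392 randomised, 20 unequal centres, ages split 50/50, R² shared equally between centre and age, permuted blocks of 4 (block size assumed), 10% random dropout, fixed centre and age in the adjusted model, 30,000 runs per R².

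| R² | SE overstated | Type I error, unadj. vs adj. | Power, unadj. vs adj. |
|---|---|---|---|
| 0 | about 0 | 4.9% vs 4.9% | 79.7% vs 79.3% |
| 5% | 1.5% | 4.6% vs 5.1% | 80.5% vs 81.5% |
| 10% | 3.8% | 4.0% vs 5.0% | 81.0% vs 83.5% |

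A second, smaller simulation (4,000 runs per setting, equal centres, three quarters of R² from centre) gave unadjusted type I error of 4.8%, 4.3% and 4.3% at R² = 0, 5% and 10%. The Monte Carlo standard error is about 0.3 points. At R² = 20% and 30%, type I error was 3.3% and 2.7%, against 5.0% and 5.4% with the strata in the model.

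**The case against.** The strongest reply is that nothing here is invalid. ANCOVA on baseline HbA1c is a legitimate pre-specified analysis, a positive result would stand, and the sample size reproduces. That is correct and limits the weight of the point.

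The assumed R² values may also be generous. With ages split 50/50 and SD 1.0, age contributes d²/4 to the variance, where d is the difference in mean change between the age groups. Split equally between age and centre, R² = 5% needs d = 2√0.025 = 0.32 points. R² = 10% needs d = 2√0.05 = 0.45 points plus a between-centre SD of √0.05 = 0.22. The whole assumed treatment effect is 0.3.

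Section 1.2 does say of statins' diabetogenic role that "risk factors include high dose, prolonged exposure, old age, prediabetic state and metabolic syndrome". That concerns diabetes risk under statins, so it points first to effect modification. Suppose atorvastatin raised HbA1c by 0.4 in older and 0.2 in younger patients, with no change on Xuezhikang. Averaged over arms, d = 0.1, R² = 0.25% and type I error is 4.97%. Even 0.6 against 0 gives d = 0.3, R² = 2.25%, type I error 4.7% and power of 80.6% against 81.2%. For centre, the protocol offers no evidence of prognostic value.

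These arguments make a small effect more likely than a large one. They do not remove the mismatch. The age term in section 8.5 belongs to a subgroup interaction model and leaves the primary analysis unchanged. A small expected gain is also a weak reason to omit the strata when including them costs almost nothing.

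**Conclusion.** The point holds. The protocol states a primary model that leaves out the factors it randomises by. Where those factors are prognostic, the test is conservative and the interval too wide. Where they are not, the test keeps its level.

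The mismatch is certain, and its size is not. Over an assumed R² of 0 to 10%, realistic conditions give a standard error overstated by 0 to about 4%, type I error between 4.9% and 4.0%, and up to about 2.5 points of power forgone. The perfect-balance formulas are the upper end, and R² near zero is quite possible. The results also rest on the assumed block size, random dropout and a residual SD of 1.0.

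There is no bias, no inflated type I error and no threat to the planned power. The change should be made because it is nearly free.

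**What to change.** In section 8.4.1 and the synopsis, specify the primary model as treatment, baseline HbA1c, age stratum (≥60, <60) as a fixed effect, and centre as a random intercept. Use the strata as recorded at randomisation. Carry the age and centre terms into the secondary endpoint models under section 8.4.2. A random intercept needs no pooling rule. If centre is fitted as fixed instead, the rule for pooling small centres must be set in advance. Should the sponsor prefer the present model, the protocol should justify omitting the strata.

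The cost is one line of model wording, using data already in the randomisation system. Fixed centre effects would use about 20 of some 350 degrees of freedom. If the strata prove not to be prognostic, the loss is about half a power point. N stays at 392. The change should be made before outcome data are seen, so that the added covariates cannot appear data-driven.

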8.4.2 Secondary endpoints

For each secondary endpoint, an ANCOVA model will be used that is similar to the one described for the primary analysis above.

8.4.3 Safety Endpoints Analyses

Adverse events are coded by using standard terminology. Subject incidences of treatment-emergent adverse events, serious adverse events, treatment-related adverse events and adverse events leading to discontinuation will be tabulated by system organ class and preferred term for each treatment group.

Subgroup analysis of AE tables by the stratification factor, gender, and age will be performed.

8.5 Subgroup analyses

In addition to the analysis described above, a set of analyses will be reported to explore whether intervention effects on the primary and secondary outcomes are consistent across subgroups of interest. These subgroups are:

- a) male vs. female,
- b) senior vs. non-senior (aged ≥ 60 at randomization vs. aged < 60),
- c) BMI $\geq 28\text{kg/m}^2$ vs. BMI $< 28\text{kg/m}^2$

For each subgroup analysis, an ANCOVA model will be used that is similar to the one described for the primary analysis above, but with additional terms identifying subgroup membership and the intervention by subgroup interaction. We will report the Hommel adjusted p-values for the interaction effects.

9 STUDY AND DATA MANAGEMENT

9.1 Site selection

Sites that do not enroll subjects within 3 months of site initiation may be closed.

9.2 Training of study site personnel

The Principal Investigator should have the professional expertise, qualifications and abilities of clinical trials, and the staff should be relatively fixed after qualification.

The investigational staff should be uniformly trained to enable researchers to fully understand the specific connotation of the clinical trial protocols and their indicators.

9.3 Monitoring of the study

9.3.1 Source data

Source data include medical record, laboratory test report and instrumental examination report. Source documents storage refers to the Clinical Study Agreement for location of source data.

9.3.2 Research Agreement

The principal investigator at each center must comply with all the terms, conditions, and obligations of the study agreement for this study. In the event of any inconsistency between this protocol and the study agreement, this study agreement shall prevail.

9.3.3 Archiving of study documents

The monitoring will identify the following:

Ensure each patient enrolled in the study has a complete folder;

Ensure informed consent of participating subjects is recorded in the folder and the process of informed consent is correct;

During the monitoring visit, the research process should be discussed with the researcher to confirm that all the procedures and operations in the protocol are performed as required;

Ensure that data are being accurately and timely recorded in the CRFs, and study drug accountability checks are being performed;

9.3.4 Deviation from the clinical study protocol

If it is necessary for the study protocol to be amended, the amendment or a new version of the study protocol must be notified to or approved by each IEC or IRB

If a protocol amendment requires a change to a particular center's Written Informed Consent Form, then principal investigator and the center's IEC or IRB must be notified. Approval of the revised Written Informed Consent Form by the IEC or IRB is required before the revised form is used.

Sponsor will distribute amendments and new versions of the protocol to investigators, who in turn is responsible for the distribution of these documents to his or her IEC or IRB, and to the staff at his or her center. The distribution of these documents to the regulatory authority will be handled according to local practice.

9.4 Study timetable and end of study

The study is expected to start in November 2021 and to end by Jul 2024.

First Subject Inclusion (FSI): July 2022

Last Subject Inclusion (LSI): July 2023

Last Subject Last Visit (LSLV): Jan 2024

Clinical study report: July 2024

9.5 Data management

9.5.1 Data from Clinical Sites

Participant Randomization: this study will use an internet-based, web browser randomization procedure. Clinical Sites access the randomization application through the study web site. Access to this application is password protected and its communications are encrypted. Once security requirements are satisfied, a series of questions identify and verify the eligibility of the participant prior to allowing randomization of the participant.

Participant Tracking: The Participant Tracking System (PTS) is a fully integrated tracking and notification system that advises clinic staff about participant follow-up windows, and projects clinic and laboratory workload for a week at a time (longer if necessary). Tracking a participant begins at screening and continues automatically throughout the project by integrating participant follow-up data with predetermined follow-up "windows". When a participant is enrolled into the study, a schedule of target dates for each of the visits is automatically generated. The report details the recommended "windows" that each visit should fall into and a case file is created for the participant.

Data Entry: The images on the data entry screens mirror the data collection forms for ease and accuracy of entry. Typically, as participant visits are completed, and hard copy forms are filled out, the clinic coordinator reviews each form for accuracy and completeness, including laboratory reports and any supporting documentation (hospital records, etc.). Once any data problems have been resolved, data are entered by clinic staff into the computer via the web-based browser application. During data entry, a variety of programmed edit checks are performed for key variables. When the edit checks fail, data may be flagged for further review or prevented from becoming part of the study database. Also, a sample of key forms may be double-keyed for additional quality control.

9.5.2 Central Database Edits

At regular intervals, data queries will be carried out on the computerized databases at the sites to perform consistency checks on key variables and forms, as a quality control check.

9.5.3 Feedback to Clinical Sites

Data edit reports will be generated to help ensure that data are entered in timely and complete manner. These reports will include both the assessment for each Clinical Site of the time between data collection and entry, and the report of

generation of missing items. These reports will be provided to the Clinical Sites, and study committees on a regular basis so that data collection items that are troublesome can be identified and Clinical Sites not meeting study standards can be notified.

9.5.4 Confidentiality

The confidentiality of all participant information must be protected at the Clinical Sites, and the CCC. Paper records and computer files must be appropriately safeguarded from unauthorized access.

Paper and/or electronic records for study participants will be stored at the Clinical Sites. Copies of records identified by participant identification number pertaining to SAEs and study-defined clinical events, including necessary medical records, will be stored at the sites. These records will receive the same care as would ordinary medical records. They will be stored in locked filing cabinets and/or filing rooms within secure office space or, if uploaded through the study website, they are stored in a non-url accessible area that can be accessed only through the website. Only study personnel who have completed training in data handling will have access to study forms.

Similar care will be used in the handling of the computer records of study data stored at each Clinical Site. Access to the data in any local database will be controlled by a system of user identification names and passwords. Each Clinical Site staff member must complete the data handling training program before being given an ID and password to use the data system. The privileges allowed to each ID can be individually specified by the local CCN Coordinator. All passwords stored within the system will be encrypted using SSL encryption.

10 REGULATORY, ETHICAL AND STUDY OVERSIGHT CONSIDERATIONS

10.1 Regulatory and Ethical Considerations

This study will be conducted in accordance with the protocol and with the following:

- Consensus ethical principles derived from Declaration of Helsinki and are consistent Chinese clinical trial research management norms and regulations.
- Applicable International Conference on Harmonization (ICH) and Good Clinical Practice (GCP) Guidelines

10.2 Ethics and regulatory review

- The protocol, protocol amendments, ICF, and other relevant documents (e.g., advertisements) must be submitted to an Institutional Review Board/Independent Ethics Committee (IRB/IEC) by the investigator and reviewed and approved by the IRB/IEC before the study is initiated.
- Any amendments to the protocol will require IRB/IEC approval before implementation of changes made to the study design, except for changes necessary to eliminate an immediate hazard to study participants.
- The investigator will be responsible for the following:
 - Providing written summaries of the status of the study to the IRB/IEC in accordance with the requirements, policies, and procedures established by the IRB/IEC
 - Notifying the IRB/IEC of SAEs or other significant safety findings as required by IRB/IEC procedures
 - Providing oversight of the conduct of the study at the site and adherence to IRB/IEC and other applicable regulations

